IND/IDE Number:	Not applicable
Participating sites:	UW Health; Madison, WI Aurora Health Care; Milwaukee, WI

Figure. MyHEART R01 Organizational Chart as submitted to NIH/NHLBI

Note: This protocol reflects the addition of the Aurora Health Care site and approval from Aurora Health Care and the Wisconsin IRB Consortium (WIC) to allow UW-Madison to serve as the IRB of record for this study. The appendix has also been updated to include Aurora site-specific recruitment and consent materials.

MyHEART is a randomized, controlled trial with two IRB-approved participating healthcare systems. The Steering Committee is the primary decision-making body for the MyHEART trial. Membership to the Steering Committee includes the study principal investigator (PI) and site-PI, lead statistician from the UW Biostatistics and Medical Informatics, research coordinators from the Wisconsin Network for Health Research, and data programmers/analysts from the UW Health Innovation Program (HIP). The ICTR Data Safety and Monitoring Committee (ICTR DSMC; <https://ictr.wisc.edu/DMC>) will serve as an independent data and safety monitoring board.

All versions of this protocol must be approved by the UW Health Sciences IRB. At the start of the MyHEART trial, study binders will be set up at each study site with the current protocol version (will include protocol number and date), and it will be available on a secure study intranet through HIP. If changes are necessary for the project, protocol modifications will be submitted to the UW Health Sciences IRB to change the protocol to fit the required changes. When the UW Health Sciences IRB approves amendments to the protocol, a copy of the approval will accompany the summary of

changes approved and the new protocol version sent to the study sites. Electronic copies of the approval documents will be forwarded to each site with the other electronic documents and stored electronically and in paper form in an IRB folder at each study site. At each WiNHR coordinator conference call, reconciliation of all current approvals will be performed by all the investigators in their study binders and electronic files.

List of Abbreviations

AE	Adverse event
AMBp	ambulatory blood pressure
ASA24	Automated Self-Administered 24-hour Dietary Assessment
BCG	Bioinformatics Computing Group
BMI	body mass index
BP	blood pressure
CARDIA	Coronary Artery Risk Development in Young Adults
cm	centimeters (used in measurements of height)
CV	cardiovascular
DASH	Dietary Approaches to Stop Hypertension diet
DBP	diastolic blood pressure
DMC	data monitoring committee
DO	doctor of osteopathic medicine
DSMB	Data Safety and Monitoring Board
DSMP	Data Safety and Monitoring Plan
eCRF	electronic case report forms
EHR	electronic health record
FDA	Food and Drug Administration
HCCQ	Health-Care Climate Questionnaire
HEDIS	Healthcare Effectiveness Data and Information Set
HIP	Health Innovation Program (at UW-Madison)
HIPAA	Health Insurance Portability and Accountability Act
ICD-10	International Classification of Disease, Tenth Edition
ICTR	Institute for Clinical and Translational Research (at UW-Madison)
IRB	Institutional Review Board
J2EE	Java 2 Platform, Enterprise Edition
JDBC API	Java Database Connectivity Application Program Interface
JNC V	The Fifth Report of the Joint National Committee on the Detection, Evaluation and Treatment of High Blood Pressure
JNC VI	The Sixth Report of the Joint National Committee on Prevention, Detection, Evaluation, and Treatment of High Blood Pressure
JNC VII	The Seventh Report of the Joint National Committee on Prevention, Detection, Evaluation, and Treatment of High Blood Pressure
kcal/kg/hr	kilo calories per kilogram per hour (used in the measurement of METs; one MET is defined as 1 kcal/kg/hr and is roughly equivalent to the energy cost of sitting quietly)
kg	kilograms (used in measurements of weight)
kg/m²	kilograms per meters squared (used in measurements of body mass index)
MD	medical doctor
MET	Metabolic Equivalent
mmHg	millimeters of Mercury (used in measurements of blood pressure)

MyHEART	My Hypertension Education and Reaching Target
NHANES	National Health and Nutrition Examination Survey
NP	nurse practitioner
OSA	obstructive sleep apnea
PA	physician assistant
PCS	Perceived Competence Scale
PI	principal investigator(s)
REALM-R	Rapid Estimate of Adult Literacy in Medicine-Revised
REDCap	Research Electronic Data Capture
SAE	serious adverse event
SBP	systolic blood pressure
SDT	self-determination theory
SV	Screening Visit
TSRQ	Treatment Self-Regulation Questionnaires
USDA	United States Department of Agriculture
UW	University of Wisconsin
WCHQ	Wisconsin Collaborative for Healthcare Quality
WIC	Wisconsin IRB Consortium
WINHR	Wisconsin Network for Health Research

[figure not shown]
Study Summary

Title	The MyHEART Study: A Young Adult Hypertension Self-Management Randomized Controlled Trial
Short Title and Precis	MyHEART R01
Protocol Number	UW-Madison HS IRB#: 2017-0372
ClinicalTrials.gov number	ClinicalTrials.gov Identifier: NCT03158051
Phase	not applicable
Methodology	Randomized controlled Trial
Study Duration	5 years
Study Center(s)	Two Healthcare Systems - UW Health (Madison, WI) - Aurora Health Care (Milwaukee, WI)
Objectives	
Aim 1. To evaluate the effect of MyHEART (home blood pressure monitor distribution and health coaching) on clinical outcomes, the change in systolic and diastolic blood pressure (primary) and hypertension control (secondary) after 6 and 12 months, compared to usual clinical care. We hypothesize that MyHEART will significantly decrease systolic and diastolic blood pressures (clinic and 24-hour ambulatory) in young adults, compared to usual clinical care.
 
Aim 2. To evaluate the effect of MyHEART on hypertension self-management behavior (behavioral outcomes) at 6 and 12 months, compared to usual clinical care. We hypothesize that MyHEART will increase the frequency of home blood pressure monitoring and lifestyle modifications (increased physical activity, decreased sodium intake).
 
Aim 3. To examine whether MyHEART's effects on self-management behavior are mediated through variables of perceived competence, autonomy, motivation, and activation (mediation outcomes). Based on our pilot study and theoretical framework, we hypothesize that MyHEART's effects will be mediated through perceived competence, autonomy, internal motivation, and patient activation.

Number of Subjects	N=340
Diagnosis	uncontrolled hypertension
Main Inclusion Criteria	18-39 years with a diagnosis of "elevated blood-pressure reading, without diagnosis of hypertension" or a hypertension diagnosis, uncontrolled blood pressure ($\geq 140/90$ mmHg), and medically homed at one of the included clinical sites
Main Exclusion Criteria	Any of the following diagnoses: chronic kidney disease, congestive heart failure, sickle cell anemia, cystic fibrosis, stroke, myocardial infarction, coronary artery revascularization, or prior/planned organ transplant; inability to provide informed consent or read or communicate in English; residence at skilled nursing or correctional facility; prescription of warfarin, novel oral anticoagulant, planned chemotherapy, planned radiation therapy, plan to move out of area in next 6 months; pregnant or plan to become pregnant in next year; illegal drug use other than marijuana in past 30 days; syncope in past 12 months
Study Product, Dose, Route, Regimen	Health coach face-to-face visits, with follow-up telephone calls, self-management support, and primary care provider feedback
FDA status of product	not applicable

Duration of administration	6-month intervention; 6-month maintenance evaluation (12-month total follow-up)
Reference therapy	Usual Clinical Care
Statistical Methodology	The primary comparisons for the co-primary outcomes of systolic and diastolic blood pressure change from baseline to 6 months will be done using analysis of covariance with MyHEART and baseline blood pressure as independent covariates. The primary comparisons for the secondary outcome of hypertension control will be based on Fisher's exact tests. Mediation analysis will be performed for Aim 3.

Schematic of Study Design

Figure: Eligibility, Enrollment, Randomization, Follow-up and Analysis

Contents

Study Summary.....	6
1 Key Roles.....	12
2 Background and Introduction.....	12
2.1 Background and Rationale.....	13
2.1.1 Development of MyHEART.....	13
2.2 Hypothesis.....	14
2.3 Study Agent.....	14
2.4 Summary of Clinical Data.....	15
2.5 Potential Risk and Benefits to Subjects.....	16
2.5.1 Known Potential Risks	16
2.5.2 Alternative to Study Participation	17
2.5.3 Protection Against Risks	17
2.5.4 Adverse Event Reporting	19
2.5.5 Potential Benefits to the Subjects	20
2.5.6 Risk Minimization	20
3 Study Design and Endpoints.....	21
3.1 General Design	21
3.1.1 Primary Study Endpoints.....	22
3.1.2 Secondary Study Endpoints.....	22
3.1.3 Primary Safety Endpoints.....	22
4 Study Subjects – Enrollment and Withdrawal.....	22
4.1 Subject Population	22
4.2 Inclusion Criteria.....	23
4.3 Exclusion Criteria	23
4.4 Subject Screening for Recruitment	24
4.4.1 Subject Identification	24
4.4.2 Recruitment and Retention Strategies	24
4.5 Vulnerable Populations	25
4.5.1 Subject Capacity	25
4.5.2 Subject/Representative Comprehension	25
4.6 Informed Consent.....	26
4.6.1 Process of Consent.....	26
4.6.2 Consent Form.....	26
4.6.3 HIPAA.....	26
4.6.4 Revoking Consent.....	27
4.6.5 Costs to the Subject	27
4.6.6 Payment for Participation	27
4.7 Early Withdrawal of Subjects	27

4.7.1	Premature termination of study	27
4.7.2	When and How to Withdraw Subjects.....	28
4.7.3	Data Collection and Follow-up for Withdrawn Subjects.....	28
5	Study Procedures	28
5.1	Prior and Concomitant Therapy	28
5.2	Randomization and Blinding of Intervention	28
5.3	Established Standard of Care	29
5.4	Study Visits.....	29

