5.2 Randomization and Blinding of Intervention

Randomization assignments for both sites will be generated by the UW Biostatistics Clinical Trials Statistical Data Analysis Center stratified by research site, in block sizes of 4 and 6 to ensure equal allocation. The Research Electronic Data Capture (REDCap) clinical data management system will be used to verify eligibility and data completeness prior to randomization. The UW Biostatistics team will develop a randomization list, which will be provided to the MyHEART research staff in a binder. There will be two people responsible for the binder at all times at HIP (PI and research manager) who will give the randomization assignment upon receiving a phone call from the

research assessor (from either site) conducting Visit 2. Until the staff receives a phone call, the binder will remain in a locked file cabinet, separate from other research materials, within a locked office at [name] (HIP).

All study participants will have contact with research staff (e.g., research coordinators, research visit study assessment staff). To reduce bias, MyHEART 6- and 12-month assessors will be blinded to treatment assignments.¹³⁰ Assessors will be trained to treat patients in both study groups identically per protocol.¹³¹ Ambulatory monitoring will be the gold standard for blood pressure measurements.

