- **Social Support** will be evaluated using a brief multi-dimensional evaluation validated for patients' chronic illnesses (example: The Medical Outcomes Study Social Support Survey).^{149,160-162}
- **Global medication adherence** will be assessed using the Morisky adherence scale.^{163,164}

Baseline Electronic Health Record and Other Database Data Collection

- **Healthcare utilization** will be evaluated using the John Hopkins Adjusted Clinical Group Case-Mix System, which assesses morbidity burden based on patient age, gender, and patterns of disease,^{50,60,66,165} the number of clinic visits will be measured.
- **Baseline antihypertensive medications and other medications:** Number of antihypertensive medication classes will account for varying hypertension treatment at baseline. Data will be acquired from the electronic health record and participant self-report, and will include prescription and non-prescription medications.
- **Primary care provider characteristics** (age, gender, specialty, time since completed medical school, % of panel with hypertension, panel size) will be obtained when available from the electronic health record and/or the American Medical Association Masterfile data.^{50,60}

Interviewer-Administered Data Collection (Baseline, 6 months, and 12 months)

- **Physical Activity.** We will assess physical activity using the Godin Exercise Questionnaire to evaluate weekly leisure activity and total leisure activity.
- **Automated Self-Administered 24-Hour (ASA24) Dietary Assessment Tool** – A web-based tool that enables multiple, automatically coded, self-administered 24-hour recalls. This tool will be used to assess, for example, sodium, fruit, and vegetable intake in relation to the DASH-sodium diet.

Blood Pressure Measurements

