6.1 Sample Size Determination

For Aim 1, approximately 930 individuals will be screened to get to a total of 340 enrolled participants (170 participants per randomized arm). This is designed under the assumption that there will be a further 15% dropout rate at the 6-month mark following randomization, to result in an effective sample size of 264.¹⁸⁴ In Nidich et al.,¹⁸⁵ the 3-month transcendental meditation program showed a mean difference of 6.3 and 4.0 in systolic and diastolic blood pressure change with a standard deviation of 13.6 and 9.7, respectively, as compared to a case of usual control among young adults at hypertension risk. With an effective sample size of 264, there is power of 0.94 and 0.87 for systolic and diastolic blood pressure, respectively, each at a two-tailed 0.025 test for an overall significance level of 0.05. For Aim 2, the effective sample size of 264 subjects will provide 90% power to detect a difference in the population mean difference from baseline to 6 months between treatment groups of about 0.4 standard deviations of the differences (moderate effect size). Aim 3 is an exploratory aim.

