6.2 Statistical Methods

See Appendix for the full Statistical Analysis Plan (SAP)

Statistical Analysis Plan Overview:

Data will be analyzed by intent to treat. Missing data will be imputed using multiple imputations.

For Aim 1, the comparisons for the primary outcomes of systolic and diastolic blood pressure change from baseline to 6 months will be done using analysis of covariance. The primary comparisons for the secondary outcome of hypertension control at 6 months will be based on Fisher's exact tests. Sequential hypothesis testing will also be performed. The 12-month analysis will focus on *maintenance* of behavior change, to assess whether significant differences seen between baseline and 6 months are retained. We will also assess the differential effectiveness of the intervention across subgroups by developing exploratory regression models.

For Aim 2, behavioral outcomes will be analyzed in a similar manner as with the clinical outcomes in Aim 1 depending on whether they are continuous or categorical. Analyses (t-tests or Wilcoxon tests and ANCOVA for continuous variables; Fisher's exact test for the categorical variable) will be performed for differences from baseline to 6 months between treatment groups. Linear or generalized linear mixed-effects regression models will be fit to describe longitudinal behavioral measurements over time.

For Aim 3, analyses will examine hypothesized mediators of the MyHEART intervention (for example, autonomy support, internal motivation, perceived competence, and patient activation). We will estimate mediation effects in multilevel models¹⁸⁶⁻¹⁹⁰ where mediation is assessed by fitting two models. Standard errors and 95% confidence intervals for the mediation effect and percent-mediated estimates will be calculated. This analysis will be pivotal to guide future replication and dissemination of MyHEART.

6.3 Planned Interim Analysis:

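### The primary ANCOVA as stated leaves out research site, the randomisation stratifier; adding it is a minor improvement at almost no cost

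*Combined protocol and SAP*

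**What the plan says.** Only the Study Summary (Statistical Methodology) lists the terms of the primary model: "analysis of covariance with MyHEART and baseline blood pressure as independent covariates". The overview in section 6.2 says that the comparison of "systolic and diastolic blood pressure change from baseline to 6 months will be done using analysis of covariance", names no covariates, and refers to a full SAP in an appendix that is not in the supplied text.

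Section 5.2 says the assignments are "stratified by research site, in block sizes of 4 and 6 to ensure equal allocation". There are two sites, UW Health in Madison and Aurora Health Care in Milwaukee. Nothing in the supplied text puts site into the primary model.

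Section 5.4.1.2, in its list of baseline data taken from health records, says: "Number of antihypertensive medication classes will account for varying hypertension treatment at baseline". It does not say in which analysis.

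Section 6.1 sets the tests "each at a two-tailed 0.025 test for an overall significance level of 0.05".

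**The concern.** Permuted blocks within site keep the arms nearly balanced at each site. A difference between sites in mean blood pressure change then largely cancels out of the arm comparison, so the true sampling error of the treatment effect is smaller than under unstratified randomisation. A model without site does not know this. It leaves the between-site difference in the residual variance and reports a standard error that is too large for the design. The intervals come out somewhat wide and each test runs below its nominal 0.025.

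The documents give some reason to expect the sites to differ. They are separate healthcare systems, section 4.1 expects higher minority recruitment at an urban site, and section 2.4 says that achieved sodium reduction differs by race and ethnicity. At stake is a little power, mainly for diastolic pressure, which has the lower stated power (0.87 against 0.94).

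**Working it through.** **Inputs from the documents (section 6.1).** Assumed effects and SDs: "a mean difference of 6.3 and 4.0 in systolic and diastolic blood pressure change with a standard deviation of 13.6 and 9.7, respectively". Sample size: "With an effective sample size of 264", taken as 132 per arm. Each test is two-sided at 0.025, so the critical value is z = 2.2414.

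**Step 1: reproduce the stated power.** Power = Φ(δ/SE − 2.2414), with SE = SD × √(2/132).

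- Systolic: SE = 13.6 × 0.12309 = 1.674; 6.3/1.674 = 3.763; Φ(1.522) = 0.936. Stated: 0.94.
- Diastolic: SE = 9.7 × 0.12309 = 1.194; 4.0/1.194 = 3.350; Φ(1.109) = 0.866. Stated: 0.87.

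Both agree (0.934 and 0.863 with the t distribution). The stated power uses the raw SD of change and takes no credit for any covariate.

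**Step 2: assumptions.** The documents give no between-site difference in change, and section 4 places accrual by site in an appendix. I assume equal site sizes (p = 0.5), SD 13.6, exact balance of arms within site, and a site difference Δ of 3, 5 or 8 mmHg in systolic change that remains after baseline adjustment. For diastolic I assume the same R², which corresponds to Δ × 9.7/13.6 = 2.1, 3.6 or 5.7 mmHg.

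**Step 3: formulas.**

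- Site R² = p(1 − p)Δ²/13.6². For Δ = 5: 0.25 × 25/184.96 = 0.0338.
- Overstatement of the SE = 1/√(1 − R²). For Δ = 5: 1/√0.9662 = 1.017.
- True size of the test without site = 2 × [1 − Φ(2.2414/√(1 − R²))]. For Δ = 5: 2 × [1 − Φ(2.280)] = 0.0226.
- Power without site = Φ[(δ/SE − 2.2414)/√(1 − R²)].
- Power with site = Φ[(δ/SE)/√(1 − R²) − 2.2414].

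| Δ (mmHg systolic) | Site R² | SE too wide by | True size at 0.025 | Diastolic power, without → with site |
|---|---|---|---|---|
| 3 | 1.2% | 0.6% | 0.024 | 0.868 → 0.871 |
| 5 | 3.4% | 1.7% | 0.023 | 0.870 → 0.878 |
| 8 | 8.7% | 4.6% | 0.019 | 0.877 → 0.897 |

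With an 80:20 site split, p(1 − p) falls from 0.25 to 0.16, and R² falls to 0.8% and 2.2% for Δ = 3 and 5.

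**Step 4: simulation.** 264 participants, two equal sites, blocks of 4 and 6 within site, residual SD 13.6, 4,000 runs per setting.

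- No site effect and no medication effect: mean SE 1.6751 without site and 1.6752 with site. Adding medication count as well gives 1.6784.
- Site effect 5 mmHg and 3 mmHg per medication class (both assumed): mean SE 1.730 without site, 1.702 with site, 1.679 with site and medication count. Type I error was 0.023, 0.025 and 0.025.

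The SE ratio 1.730/1.702 = 1.017 matches the formula. The Monte Carlo error of a simulated size near 0.025 is √(0.025 × 0.975/4000) = 0.0025, so the size figures rest on the formula; the simulation is only consistent with them.

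**The case against.** The strongest reply is that the omission is not shown for the whole plan. The Study Summary gives one sentence and does not say that its list is complete, and the SAP appendix may already include site. This stands as a limit on scope: the point concerns the model as stated in the Summary and left unspecified in section 6.2.

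The second reply is that every size above is assumed. That also stands. An 8 mmHg site difference in change would exceed the 6.3 mmHg design effect, and an unequal site split shrinks the figures. Dropout loosens the balance within site, which brings the unadjusted standard error closer to correct. The different coaches are not a good argument for a site term either. Coaching is given only in the intervention arm, so coach differences act mainly as site-by-arm effects, which a site main effect does not model.

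Two stronger readings are tempting. A reader might infer that leaving out baseline antihypertensive classes also makes the intervals too wide. It does not: medication count was not a stratifier, so the intervals stay valid without it and may only be less precise. A reader might also infer that the primary model breaks a commitment in section 5.4.1.2. That sentence explains why a variable is collected and names no model or outcome. It could be met by baseline reporting, the imputation model or the exploratory regressions in section 6.2.

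None of this gives a reason to leave site out.

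**Conclusion.** The point holds for site, as a minor and essentially free improvement. The model in the Summary does not include the factor that section 5.2 uses to stratify. If site predicts change given baseline pressure, reported precision is understated by roughly 0.6% to 4.6% of the standard error over the assumed range, and diastolic power is lower than it need be by 0.3 to 2.0 percentage points. If site predicts nothing, nothing is lost by omitting it and nothing by including it.

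The error is in the conservative direction. It creates no excess false-positive risk and does not undermine a positive result, and the stated power of 0.94 and 0.87 does not depend on it. The documents do not establish that precision will be lost, only that it may be. Confidence is high that the stated model lacks site. It is low on the size of the effect, and the content of the SAP appendix is unknown.

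**What to change.** In the Study Summary, section 6.2 and the SAP, give one identical statement of the primary model for each of systolic and diastolic pressure: ANCOVA of 6-month change on arm, the matching baseline pressure and research site. If the SAP appendix already includes site, only the Summary and section 6.2 need to be aligned with it.

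Optionally, pre-specify the number of baseline antihypertensive classes as a further covariate in the primary blood pressure model or in a sensitivity analysis, and say in section 5.4.1.2 which analysis uses it. Nothing here supports carrying that covariate over to the Aim 2 or 12-month analyses as a blanket rule.

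The cost is a line of wording and one degree of freedom for site. Site is known for every participant and medication classes are already collected. The change should be made before outcomes are compared by arm. The documents do not show how far the trial has progressed; if that comparison has already been made, keep the stated model as primary and report the site-adjusted model as a dated sensitivity analysis.
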